#### 5.4 Outcomes definitions

**Degree of difficulty:** Difficult ETT placement is the primary outcome defined as: (i.) either first intubation time >60 seconds or (ii.) first attempt failure at intubation or (iii.) ease of intubation reported as difficult by the provider dichotomized by a scale score of 4 or 5 versus 1, 2, or 3.

**Control group-FIS placement:** A successful attempt will be defined as when the insertion tip of the FIS enters the patient's mouth (or nose), leading to placement of the ETT into the trachea and confirmation of the end-tidal CO2 capnography waveform. Any other manipulation of the airway leading to incorrect placement of the ETT will be considered a failed attempt.

**Intervention group-VL/FIS placement:** A successful attempt will be defined as when the tip of the video laryngoscope blade and insertion tip of the FIS enters the patient's mouth, leading to placement of the ETT into the trachea and confirmation of the end-tidal CO2 capnography waveform. Any other manipulation of the airway leading to incorrect placement of the ETT will be considered a failed attempt.

**Difficult intubation:** The subjective level of difficult ETT insertion termed "Ease of Intubation" measured on a Likert scale from 1 to 5, with 1 being "Extremely Easy" and 5 being "Extremely Difficult."

**Ease of ETT insertion:** The subjective level of ease of ETT passage thought glottis (from 1 = *Extremely Easy* to 5 = *Unsuccessful*) in the performance of the randomized intubation technique (FIS vs VL/FIS) will be recorded.

**Incidence of desaturation:** Incidence of oxygen saturation  $\leq 92\%$  will be recorded.

**Degree of Irritation:** The subjective level of irritation provided by the patient (0 = *None*; 1= *Mild*; 2 = *Moderate*; 3 = *Severe*) perioperatively (both pre and post operatively) will be recorded.

**Total Time:** The total time from the beginning of either FIS or FIS/VL combination insertion until successful ETT intubation in seconds, as verified by capnographic waves, chest rise and fall, and fogging of the ETT will be recorded.

**Total Score:** Outcomes for each of the 3 items: i) time of intubation, ii) number of attempts, and iii) the number of complications, a total score will be derived for each patient. Each outcome will be translated into a binary scale. For example, starting with intubation time, the completion a procedure within 60 seconds will be assigned a '0', and completion taking more than 60 seconds will assign a '1'. For the number of attempts, we will assign a '0' for a single attempt and a '1' for more than a single attempt. And finally for complications, we will assign a '0' for no complication arising and a '1' for any complications arising. The total score will range from 0 to 3.

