### 2.6 Rationale

Combined VL and FIS can provide superior conditions for tracheal intubation in patients with head and neck tumors. We hypothesize that the use of the combination technique will improve the time to intubation and also decrease the number of attempts to intubate head and neck patients with known or suspected difficult airways. If our hypothesis is confirmed, a significant large number of patients will benefit (i.e. less trauma, less episodes of hypoxemia and less postoperative sore throat) from the use of this new intubation technique. To test our hypothesis, we plan on conducting a randomized controlled trial using the combination of FIS with VL, comparing it to the use of the FIS alone in patients with known or suspected difficult airways undergoing surgical procedures.

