### **5.3 Measurements**

Morphometric characteristics and airway assessments of all patients will be recorded in the preoperative holding area. Patients will be asked questions to assess degree of irritation. Baseline measures of blood pressure, pulse, oxygen saturation, and End-Tidal CO2 will be recorded prior to induction. Vital signs will be recorded during preoxygenation, before induction of anesthesia, after induction of anesthesia, during laryngoscopy and/or bronchoscopy, after successful intubation, and 3 times while in recovery (at PACU arrival, at 30 and 60 minutes after PACU arrival). Lastly, we will ask the same questions to the patients about degree of irritation when they're fully awake. Additionally, the anesthesiologist will provide a personal, subjective assessment following successful or failed/rescue intubation with the corresponding research procedure/technique.

**Intubation technique:** Although the time required for successful intubation is not a primary endpoint for the study, the time and number of attempts required for successful tracheal intubation will be recorded for each patient. The glottis view obtained will be recorded using the percentage of glottis opening (POGO) score. If the epiglottis is down folded and a jaw lift is required to improve view, this information will be reported. The view both before and after jaw lift will also be recorded using the POGO score. If blood or secretions are present and require suctioning, time will be stopped while suctioning occurs and this will be recorded. If rotation of the ETT to obtain intubation is required or esophageal intubation occurs, this will also be recorded. The subjective level of difficulty in the performance of intubation will also be recorded.[2]

**Intubation:** We will record how long in seconds and number of attempts required for successful endotracheal intubation in each group. An attempt is defined as an attempt at placement of an ETT through the glottic opening, pass the vocal cords, and into the trachea. Removal/reinsertion of the laryngoscope/fiberoptic scope will constitute as a new attempt. If more than 2 attempts are needed or if the anesthesia provider discontinues protocol procedures, for any reason, the case will be deemed a failure.

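### Does the 60-second criterion in the primary outcome lack a clock, and does VL/FIS lack a start time?

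*Combined protocol and SAP*

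**What the plan says.** Section 5.4 (Degree of difficulty) makes the primary outcome a yes/no composite. A placement is difficult on "first intubation time >60 seconds or (ii.) first attempt failure at intubation", or if the provider scores ease of intubation 4 or 5 on a five-point scale. First intubation time is not defined as a separate term.

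The same section defines Total Time as "The total time from the beginning of either FIS or FIS/VL combination insertion until successful ETT intubation in seconds", with its end point "as verified by capnographic waves, chest rise and fall, and fogging of the ETT will be recorded". For the intervention arm it describes a successful attempt as one in which "the tip of the video laryngoscope blade and insertion tip of the FIS enters" the mouth and the tube is then placed and confirmed by capnography. The control arm has the parallel description with the scope only.

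Section 5.3 (Measurements) adds a pause rule: "If blood or secretions are present and require suctioning, time will be stopped while suctioning occurs and this will be recorded". It also defines when a fresh attempt begins: "Removal/reinsertion of the laryngoscope/fiberoptic scope will constitute as a new attempt". Its paragraph on technique opens with "Although the time required for successful intubation is not a primary endpoint for the study", while Section 2.6 states "We hypothesize that the use of the combination technique will improve the time to intubation".

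**The concern.** The 60-second cut is one of three routes to the primary outcome, yet nothing in Section 5.4 says that it is measured on the Total Time clock or that the suction pause in Section 5.3 applies to it. With FIS alone there is one device and so one possible time zero. With VL/FIS, timing could be started at blade entry or at scope entry.

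A single patient shows what is at stake. Suppose the blade enters at 0 s, the scope at 10 s, and placement is verified at 65 s on the first attempt, with an ease score of 3. Timed from the blade this is 65 s, hence difficult. Timed from the scope it is 65 − 10 = 55 s, hence not difficult. Any such interval exists in one arm only, so leaving it out would lower the VL/FIS rate and leave the FIS rate alone.

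Four lesser points seem to add to this:

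- A successful attempt is confirmed by capnography, whereas Total Time ends on capnography, chest movement and tube fogging.
- The exploratory Total Score uses a 60-second cut without naming a clock.
- Withdrawing a device before any tube pass is not expressly called a first-attempt failure.
- Section 5.3 says time is not a primary endpoint, although a time cut is part of the primary outcome.

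**Working it through.** **1. The plan's own figure.** Inputs from Section 10.1: 60 per arm, 30% against 10%, two-sided chi-square test, alpha 0.05. With the pooled normal approximation:

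- mean rate = (0.30 + 0.10)/2 = 0.20
- null term = √(2 × 0.20 × 0.80) = 0.5657
- alternative term = √(0.30 × 0.70 + 0.10 × 0.90) = 0.5477
- z = (0.20 × √60 − 1.96 × 0.5657)/0.5477 = 0.804, so power = 78.9%

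Exact enumeration of the uncorrected test gives 80.2%. The stated 80% is reproduced, and it does not depend on the timing wording.

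**2. Where the time ground can decide the class.**

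| First attempt | Ease score | Class | Does the clock matter? |
|---|---|---|---|
| Fails | any | difficult by (ii) | no |
| Succeeds | 4 or 5 | difficult by (iii) | no |
| Succeeds | 1, 2 or 3 | decided by (i) | yes |

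Only the third row depends on the clock. Those patients had one attempt, so Total Time covers that attempt and nothing else. First intubation time and Total Time are then the same interval, and the missing cross-reference has no consequence.

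**3. Which event starts Total Time in VL/FIS.** The definition starts at the beginning of inserting the combination. Inserting two devices begins when the first one goes in. To start at scope entry, one must read the beginning of the insertion as its completion. The sentence that mentions both tips defines a successful attempt, not a timer, and sets no competing start. The suction pause is stated generally, in the paragraph on recording intubation time, and covers both arms.

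**4. Can the alternative reading be sized?** The documents give no blade-to-scope interval and no distribution of times, so any figure rests on assumptions. Suppose times from blade entry are lognormal with log-SD 0.5, a share b of VL/FIS patients exceeds 60 s, and the gap is g seconds. The shift is b − P(T > 60 + g).

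- b = 5%, g = 3 s: median 26.4 s, shift 0.93 points, or 0.0093 × 60 = 0.6 patients
- b = 10%, g = 15 s: median 31.6 s, shift 5.80 points, or 0.058 × 60 = 3.5 patients

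The upper figure needs the time ground alone to account for the entire planned 10% rate. If half of the shifted patients were already difficult on (ii) or (iii), the range would halve to 0.3 to 1.7 patients.

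**5. What a few patients would do to the test.** Uncorrected chi-square with 18 of 60 in FIS:

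| VL/FIS difficult, of 60 | p |
|---|---|
| 6 (planned 10%) | 0.006 |
| 7 | 0.013 |
| 8 | 0.027 |
| 9 | 0.049 |
| 10 | 0.084 |

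For the first row, z = 0.20/√(0.20 × 0.80 × 2/60) = 2.74. From the planned rates, moving one or two patients leaves the result significant. One patient is decisive only for a result already at the boundary, which is true of any misclassification.

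**6. The lesser points.** All four are worded alike for both arms.

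- Chest movement and fogging are further verification of the placement that capnography confirms; the two sentences do not contradict each other.
- The Total Score cut is exploratory and stands in the section that defines the only clock.
- If a reinsertion counts as a new attempt, the attempt before it did not succeed.
- Time as a measured quantity is a secondary objective in Section 1.2, whereas the primary outcome is a binary composite that uses a time threshold. The Section 5.3 sentence is loose but compatible, and Section 2.6 states a hypothesis, not an endpoint.

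**The case for a change.** The best case for acting is that the sensible reading takes two inferences: that the time ground uses Total Time, and that inserting the combination begins with whichever device goes in first. A component of the primary outcome should not rest on inference when one sentence would settle it. The provider knows the allocation (Section 5.2), so blinding does not protect a start left to judgment. The one-sided direction is also real: timing from scope entry could only help the intervention.

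The omission itself stands: the cross-reference is absent and the starting device is not named. The direction of the possible bias is also correctly described. What does not follow is that a stated rule gives a wrong result. Both inferences are the ordinary sense of the words, and no passage supplies a rival clock. Section 11.1 says that staff review data-collection instructions, and Section 11.4 refers to a paper case report form. Neither is available here, so it cannot be shown that the study lacks an operational start rule, nor that it has one.

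**Conclusion.** No change to the plan is called for. The wording is incomplete, but it can be applied as it stands: first device in, to verified placement, with suction time excluded. Applied throughout, that reading creates no arm-specific shift and leaves the sample size and power as stated. A written definition would record what staff would sensibly do anyway. The conclusion rests on two readings: that Total Time is the clock for the time ground, and that inserting a two-device combination begins with the first device. If timing were in practice started at scope entry, the VL/FIS rate would be lowered by an amount that the documents do not allow one to derive. The range in the check above is illustration and not evidence of bias. The four lesser points are matters of wording and affect both arms alike.

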#### **Research Procedure (Intervention group-VL/FIS)**

Following induction of general anesthesia and adequate manual ventilation, the anesthesia provider will attempt to successfully intubate the patient utilizing both, a video laryngoscope and a flexible intubation scope. No more than 2 intubation attempts shall be made. If necessary, between intubation attempts, adequate patient ventilation will occur before the next attempt.

For both the control and intervention groups, the anesthesia provider will be given the option to secure the airway via oral pathway (passage) according to clinical judgment. If a patient's airway has not been secured within the two attempts of the respective, allocation treatment, a third attempt will be made utilizing another technique or device (as a rescue attempt) at the discretion of the anesthesia provider. At this point, no further study data will be collected, except of what device was used for the rescue attempt and any potential Adverse Events.

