## **10.2 Planned Statistical Analysis**

For the Secondary Objective:

To evaluate ease of use, each of the 3 dimensions described below will be assessed independently. First, the time of intubation will be assessed for distributional assumptions using histograms, stem and leaf plots, and box plots. Descriptive statistics such as the median and range or the geometric mean  $\pm$  SD will be used to summarize the data. Second, ordinal data describing the number of attempts will be summarized using the median and range; and third, the number of complications will be summarized using the median and range. For number attempts and complications, frequencies and percentages will be used if the maximum number is small ( $\leq$  4 attempts or complications). Comparisons between continuous covariates of interest will be conducted using a t-test, or Wilcoxon rank-sum test if more appropriate. Categorical covariates will be compared using chi-square or Fisher's exact test.

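### The Total Score's attempts item codes a case abandoned after one attempt like a first-pass success, and failed cases have no defined value in the attempt count or the time item

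*Combined protocol and SAP*

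**What the plan says.** Section 5.2 limits the allocated technique in both arms: "No more than 2 intubation attempts shall be made". If the airway is still not secured, "a third attempt will be made utilizing another technique or device (as a rescue attempt) at the discretion of the anesthesia provider". From then on the study records only the rescue device and any adverse events.

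Section 5.3 records the time and the "number of attempts required for successful endotracheal intubation in each group". A case is a failure if more than two attempts are needed. It is also a failure on a second ground: "if the anesthesia provider discontinues protocol procedures, for any reason, the case will be deemed a failure".

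Section 5.4 builds the Total Score from three binary items, and Section 10.3 repeats it.
- **Attempts:** "we will assign a '0' for a single attempt and a '1' for more than a single attempt".
- **Time:** "the completion a procedure within 60 seconds will be assigned a '0', and completion taking more than 60 seconds will assign a '1".
- **Complications:** 0 for none, 1 for any. Failed intubation is not listed as a complication.

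Total Time in Section 5.4 runs until successful intubation. Number of attempts is a secondary objective (Section 1.2) and one of the three ease-of-use dimensions in Section 10.2. The usefulness of the Total Score is the exploratory objective (Section 1.3).

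**The concern.** The attempts item looks only at how many attempts were made, not at whether any succeeded. Section 5.3 allows a case to become a failure after a single attempt, because the provider may stop for any reason. The two rules together put that failure in the favourable category.

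The other measures have a gap rather than a wrong code. The attempt count is the number needed for success, and the time item grades only a completed procedure. Neither says what a failed case receives, so the analyst would have to choose after seeing the data. Leaving the values missing would drop the failures from the comparison.

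The provider knows the allocation (Section 5.2) and decides when to stop, so early abandonment could differ between arms. If it does, the arm with more of it looks better on the attempts item for that reason alone.

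**Working it through.** **The plan's own figures.** The plan states no figure for the attempt count or the Total Score. Its one power figure, for the primary outcome, reproduces. With 60 per arm, 30% v 10% and two-sided alpha 0.05:

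Φ[(0.20·√60 − 1.96·√(2·0.2·0.8)) / √(0.3·0.7 + 0.1·0.9)] = Φ[(1.549 − 1.109)/0.548] = Φ(0.80) = 0.789, against the stated 80%. Nothing below touches that calculation.

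**Applying the scoring rules to each possible outcome.** Inputs are the cap of two (5.2), the failure definition (5.3) and the three items (5.4). Total Score = attempts item + time item + complications item.

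| Outcome with the allocated technique | Attempts item | Time item | Total Score, no / any complication |
|---|---|---|---|
| Success on attempt 1, within 60 s | 0 | 0 | 0 / 1 |
| Success on attempt 1, over 60 s | 0 | 1 | 1 / 2 |
| Success on attempt 2, within 60 s | 1 | 0 | 1 / 2 |
| Success on attempt 2, over 60 s | 1 | 1 | 2 / 3 |
| Failure after two attempts | 1 | not defined | 1 / 2 if time is coded 0; 2 / 3 if coded 1; otherwise missing |
| Discontinued after one attempt (a failure) | **0** | not defined | 0 / 1 if time is coded 0; 1 / 2 if coded 1; otherwise missing |

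The last row shows the error: the attempts item is 0 by the stated rule. The last two rows show the gap in the time item. The raw attempt count of a failure is likewise open. It could be the attempts made, 3 if the rescue attempt is included, or missing.

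**How much two cases can matter.** The counts are assumptions, since the documents give no abandonment rate. Suppose 18 control and 8 intervention patients, of 60 each, need a second attempt or fail. The uncorrected chi-square for a 2×2 table is N(ad − bc)² / (product of the four margins).
- 18 v 8: 120·(18·52 − 42·8)² / (60·60·26·94) = 4.91, p = 0.027 (Fisher 0.045).
- If two of the 18 were abandoned after one attempt and so coded 0, 16 v 8: 120·(16·52 − 44·8)² / (60·60·24·96) = 3.33, p = 0.068 (Fisher 0.109).

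The observed difference falls from 10/60 = 16.7 to 8/60 = 13.3 percentage points. The item has no stated alpha or power, so the change in p-value shows sensitivity only.

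**Would separate categories and a rank test be enough?** Suppose 12 patients per arm use two attempts, and 10 v 2 of them are never intubated with the allocated technique.
- More than one attempt, 12 v 12: p = 1.0.
- Failure, 10 v 2: chi-square 5.93, p = 0.015 (Fisher 0.029).
- Wilcoxon rank-sum on first-attempt success / second-attempt success / failure, 48/2/10 v 48/10/2. The midranks are 48.5, 102.5 and 114.5. The first arm's rank sum is 48·48.5 + 2·102.5 + 10·114.5 = 3678, against 3630 expected. The tie-corrected standard deviation is 132.8, so z = 48/132.8 = 0.36 and p = 0.72.

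Three categories make the difference visible in a table, but the rank test does not detect it. The comparison of failure rates does.

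**The case against.** The strongest reply is that no single measure has to carry failure. First-attempt failure is a component of the primary outcome, the rate of failure is a secondary objective, and the ease-of-insertion scale ends at 5 for unsuccessful. The three ease-of-use dimensions are assessed separately, and the Total Score is only exploratory. All of this stands and limits the severity. It does not change the code that the attempts item gives to an abandoned case.

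A reader might also infer four stronger things that the documents do not support.
- *That every two-attempt failure counts 2, like a second-attempt success.* The raw count is defined by success, so its value for a failure is undefined rather than certainly 2.
- *That the Total Score gives an abandoned case its best value.* That needs the time item coded 0 and no complication, and the plan gives no time code for a case without completion.
- *That these measures cannot reflect ease of intubation.* They still order the successful cases, which may be most of the trial.
- *That the summary "ordinal data describing the number of attempts will be summarized using the median and range" misfits a variable capped at two.* Section 10.2 switches to frequencies and percentages when the maximum is at most 4, so the suitable summary is already selected.

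It is also fair to say that no document shows abandonment will differ between arms. The bias is a possibility that the rule permits, not a demonstrated effect.

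**Conclusion.** Wrong as written, minor severity. The attempts item gives a case discontinued after one attempt the same code as a first-pass success, although Section 5.3 calls that case a failure. That follows from the text without any assumption. For all failures, the time item, Total Time and the attempt count have no defined value.

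The size depends on how often providers stop after one attempt, which the documents do not say. With no such cases the miscoding has no effect and only the gap for two-attempt failures remains. In the assumed example, two cases reduce the difference by 2/60 = 3.3 percentage points. The direction favours whichever arm has more early abandonment.

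The consequences are limited to the attempt count (secondary) and the Total Score (exploratory). The primary outcome and the sample size are unaffected.

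**What to change.** 1. In Sections 5.4 and 10.3 and the matching summary-table text, assign 1 on both the attempts item and the time item to every case deemed a failure under Section 5.3, whatever the number of attempts made.
2. In Section 10.2, report attempts in three categories with frequencies and percentages: success on attempt 1, success on attempt 2, failure of the allocated technique. State that the rescue attempt is not counted.
3. Compare the failure rate between arms alongside, with the chi-square or Fisher test already named. A rank test on the three categories may miss a difference confined to failures.

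The cost is wording only, because attempts and failure status are already recorded. There are two small downsides. The item becomes attempts or failure rather than a pure count. The binary item also still ties a second-attempt success with a failure, which is why the failure rate must be shown next to it.
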